### **Background, Rationale and Context**

Enoxaparin is a factor Xa inhibitor commonly used for both prophylaxis against and treatment of thromboembolism. It is also frequently used off-label as a perioperative bridge for patients that are chronically anticoagulated prior to surgery, such as those taking Warfarin. It is an attractive option for perioperative use secondary to its predictable pharmacologic profile and the lack of recommended routine blood monitoring. Therefore, it is common to encounter a patient who has recently received a treatment dose of Enoxaparin prior to presenting for surgery. For these patients, and those on other anticoagulant medications, published guidelines have been developed to help guide clinical decision-making when the anesthetic/analgesic plan includes regional anesthesia.

Currently, these guidelines recommend that a minimum of 24-hours should elapse following the last treatment dose of Enoxaparin before a neuraxial procedure is performed. However, a recently completed quality improvement project conducted at Wake Forest Baptist Medical Center found that almost 60% of patients presenting for surgery while on treatment dose enoxaparin still had significant anticoagulant activity 24-hours following their last dose, as demonstrated by anti-Xa level assay testing. Given that the risk of epidural hematoma formation is increased in the setting of abnormal coagulation parameters, the significance of this finding is that the risk of bleeding complications following a neuraxial procedure may still be increased 24-hours after the last treatment dose of enoxaparin.

While the routine use of anti-Xa level testing may be a viable option to determine when residual enoxaparin activity is present before proceeding with a neuraxial procedure on a patient-by-patient basis, it is not universally available at all hospitals. Therefore, it is important to determine the time interval following the last enoxaparin dose at which the likelihood that a clinically relevant amount of residual anti-Xa level activity no longer persists, so that providers can confidently proceed with a neuraxial procedure when anti-Xa level testing is not available.

### **Objectives**

The main objective of this study is to determine the time interval following the last treatment dose of enoxaparin at which the amount of anti-Xa level activity is reliably less than 0.2IU/mL in patients presenting for elective surgery.

### **Methods and Measures**

#### **Design**

- This is a randomized prospective observation trial.

#### **Setting**

- This study will be conducted at a single institution (Wake Forest Baptist Medical Center), which is an academic level-1 trauma center.

### **Subjects selection criteria**

Protocol version:

Template updated 9.24.14

Patients presenting for elective surgery who are either chronically on treatment-dose enoxaparin or who are being bridged with treatment-dose enoxaparin from another anticoagulant will be potentially recruited for this investigation.

- **Inclusion Criteria**

Eligible patients need to be on treatment dose (1mg/kg twice daily or 1.5mg/kg daily) enoxaparin at the time of presentation for elective surgery and must be able to accurately report the timing of their last dose and the administered dosage. Patients must also be between the ages of 18-100 years of age and must be able to give written consent to participate. Patients who are bridged with enoxaparin from one of the currently available oral Anti-Xa inhibitors (Abixaban [Eliquis], Edoxaban [Sayvasa], and Rivaroxaban [Xarelto]) will be eligible as long as the duration from their last oral Anti-Xa inhibitor dose to their date of surgery is at least 5 days (120-hours).

- **Exclusion Criteria**

Patients with severe renal insufficiency (creatinine clearance <30ml/min) will be excluded from the study, as the elimination of enoxaparin is known to be affected in this patient population. Pregnant patients will also be excluded, as the elimination and metabolism of enoxaparin is known to be altered in this patient population, and dose adjustments are recommended if treatment dose enoxaparin is used during pregnancy. Patients who are receiving enoxaparin as a bridge from another intravenous anti-Xa inhibiting medication will be excluded as this could unpredictably affect the results of anti-Xa testing. These medications include: Fondaparinux. Patients who are on an oral Anti-Xa inhibitor (Abixaban [Eliquis], Edoxaban [Sayvasa], and Rivaroxaban [Xarelto]) will be excluded if the duration of time from their last dose to the date of surgery (i.e., the duration that they are bridged with enoxaparin) is less than 5 full days (120 hours).

- **Sample Size**

Historical data from a previous publication (which showed that at 24-hours 58% of patients had an anti-Xa level  $\geq 0.21\text{IU}/\text{mL}$ ) was used to conduct a power analysis. In this prior study, data points were collected between 23.25-hours and 32-hours, and anti-Xa levels ranged between 0 and  $0.54\text{IU}/\text{mL}$ . Assuming a similar relationship between anti-Xa activity levels and time observed in the original study pertains to later times, simulations using a sample size of 150 patients resulted in a threshold of approximately 29-hours with 95% confidence limits of approximately 28-hours and 33-hours. It was felt that a 5-hour window of the 95% confidence limit would provide acceptable guidance for clinical care. We expect some drop out and patient loss since some patients may have their surgical procedure cancelled following enrollment/randomization. In addition, occasionally the decision regarding the use of bridging therapy changes following a patient's visit to the preoperative assessment clinic. Therefore, we plan to enroll upwards of 180 patients until 150 patients have completed the study and have their data available for analysis.

### **Interventions and Interactions**

- Patients on treatment dose enoxaparin will be identified at the time of their preoperative anesthesia consultation. These patients will be seen in the preoperative assessment clinic by a study team member and the study will be discussed with them at that time.
- Patients may elect to consent during their preoperative anesthesia consultation visit, or if they would like to think it over and talk with family/friends, a study team member will follow-up with them by phone to answer further questions.
- After consenting to the study, patients will be randomized to one of two groups.
  - Group one will be instructed to administer their last dose of enoxaparin at 07:00 in the morning on the day prior to their scheduled surgery date. This will mean

Protocol version:

Template updated 9.24.14

that patients who have their surgery scheduled for 07:00 the following day will be 24-hours removed from their last dose. Patients presenting for surgery later in the day would be slightly farther removed from their last dose, however this is currently considered normal clinical practice.

- Group 2 will be instructed to administer their last dose of enoxaparin at 19:00 in the evening two days prior to their scheduled surgery date. Patients presenting for surgery at 07:00 two days later will be 36-hours removed from their last dose. Patients presenting for surgery later in the day would be slightly farther removed from their last dose, but again this mimics normal clinical practice in which the timing of the last dose of self-administered enoxaparin is not routinely adjusted based on the scheduled surgical start time.
- All patients consented for the study will be called by a study team member or study coordinator two days before their surgical date to ensure they understand when they are supposed to self-administer their last dose of enoxaparin.
- Upon arrival for surgery, all consented patients will have demographic information recorded (age, weight, gender) as well as the enoxaparin dosage and the timing of their last administration.
- All patients in the study will have a blood sample drawn. Two laboratory tests will be sent.
  - 1). Anti-Xa level assay (Heparin Assay)
  - 2). Basic Metabolic Panel (BMP) (for evaluation of creatinine).
- When feasible, blood sampling will be performed at the same time that intravenous access for fluid/medication administration is obtained to minimize patient discomfort.
- Anti-Xa level testing will be performed using a chromogenic assay and a hybrid heparin/enoxaparin curve (Biophen Heparin 6 kit).
- The results of both of these tests will be collected from the electronic medical record after the results are posted.
- Following collection of the blood samples, the patient's participation in the study will be concluded.
- The results of the anti-Xa level test will be shared with the patient and the risk-benefit decision of proceeding with neuraxial block (if indicated) will be left to the anesthesiologist of record.

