## **Human Subjects Protection**

### **Subject Recruitment Methods**

Patients on treatment dose enoxaparin will be identified at the time of their preoperative anesthesia consultation. These patients will be seen in the preoperative assessment clinic by a study team member and the study will be discussed with them. They will be given information related to the study (consent form). Patients may elect to consent to participation that day, or a study team member will follow-up with them by phone two days before their surgery to answer questions. If they choose to participate at that time the consent paperwork will be completed the day of surgery, but they will be randomized and instructed on when to self-administer their last treatment dose of enoxaparin prior to surgery.

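### Patients who defer consent are randomised on the day of Group 2's 19:00 last dose, so a once-daily user who injected that morning can comply only by taking a second full dose

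*Combined protocol and SAP*

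**What the plan says.** Day 0 is the day of surgery, day -1 the day before, and so on.

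- **Eligible regimens** (Subjects selection criteria): "Eligible patients need to be on treatment dose (1mg/kg twice daily or 1.5mg/kg daily) enoxaparin at the time of presentation for elective surgery". The population is patients "either chronically on treatment-dose enoxaparin or who are being bridged with treatment-dose enoxaparin from another anticoagulant", so it includes people with a long-established injection habit.
- **Last-dose times** (Interventions and Interactions): "Group one will be instructed to administer their last dose of enoxaparin at 07:00 in the morning on the day prior" and "Group 2 will be instructed to administer their last dose of enoxaparin at 19:00 in the evening two days prior". The two times apply to everyone and are not adapted to the regimen or the usual injection time.
- **Deferred consent** (Subject Recruitment Methods): for a patient who does not decide in clinic, "a study team member will follow-up with them by phone two days before their surgery to answer questions". If the patient agrees at that call, the paperwork is signed on the day of surgery, "but they will be randomized and instructed on when to self-administer their last treatment dose of enoxaparin prior to surgery".
- **Recorded on arrival** (Interventions and Interactions): demographic items "as well as the enoxaparin dosage and the timing of their last administration". The dose before the last one is not listed.

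No visible section gives a time of day for the call, or says what to do if that day's dose has already been taken. The data collection form and consent form are named in the Appendix but were not available for this review.

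**The concern.** The two assigned times are 12 h apart, which suits a twice-daily schedule. For a once-daily user, one of them will usually be far from the habitual time. A patient who learns the assignment early enough can move the preceding dose. On the deferred route that may no longer be possible, because for Group 2 the call, the randomisation and the last dose all fall on day -2. A once-daily morning user may have injected before the phone rings.

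That patient has three options. A second full dose at 19:00 meets the instruction. Stopping after the morning dose, or taking the usual dose on day -1, misses it. At stake are an avoidable extra dose of anticoagulant arising from a study instruction, and an unplanned departure from the assigned interval. The group affected is narrow. Twice-daily users are not caught, because 19:00 is at or near their next usual dose. Evening once-daily users assigned to Group 1 are not caught if the call comes before their day -2 dose, since that dose can still be moved.

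**Working it through.** **The plan's own intervals.** From 19:00 on day -2 to 07:00 on day 0 is 5 + 24 + 7 = 36 h. From 07:00 on day -1 to 07:00 on day 0 is 24 h. Both match the protocol.

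**Intervals for a once-daily morning user, already injected on day -2, assigned to Group 2.** Let *u* be the usual clock hour. The range 06:00 to 10:00 is an assumption; 07:00 is the protocol's own morning time.

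- Gap to a second dose at 19:00: 19 - *u*
- Stops after the morning dose, hours to a 07:00 surgery: 48 + 7 - *u*
- Takes the usual dose on day -1, hours to a 07:00 surgery: 24 + 7 - *u*

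| Usual time | Gap to 19:00 dose (h) | Stops: hours to surgery | Doses on day -1: hours to surgery |
|---|---|---|---|
| 06:00 | 13 | 49 | 25 |
| 07:00 | 12 | 48 | 24 |
| 08:00 | 11 | 47 | 23 |
| 09:00 | 10 | 46 | 22 |
| 10:00 | 9 | 45 | 21 |

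Only the second column keeps the 36 h target. The last column is in effect Group 1 timing.

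**Dose.** Two doses of 1.5 mg/kg make 3.0 mg/kg within 9 to 13 h. That is 3.0/1.5 = 2 times this patient's daily total, and 3.0/2.0 = 1.5 times the daily total of the twice-daily regimen.

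**Number of patients.** The documents give none of the shares needed. Assumed ranges: once-daily 5% to 30%; established morning habit 25% to 75%; deferred route 10% to 50%; allocation 1:1. Every call is assumed to follow the injection.

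- Low: 180 x 0.05 x 0.25 x 0.10 x 0.5 = 0.1
- Midpoints: 180 x 0.175 x 0.50 x 0.30 x 0.5 = 2.4
- High: 180 x 0.30 x 0.75 x 0.50 x 0.5 = 10.1

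These count patients who face the conflict, not patients who take the extra dose.

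**Effect of an extra dose on the measured level.** Assume first-order decline with a half-life *t* of 5 to 7 h (not in the documents), and write r(h) = 2^(-h/*t*). Relative to a regular 24 h schedule, a final dose taken *g* hours after a full dose multiplies later levels by 1 - r(24) + r(*g*).

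- *t* = 5 h: 1.251 (*g* = 9) to 1.129 (*g* = 13)
- *t* = 7 h: 1.317 (*g* = 9) to 1.183 (*g* = 13)

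The level thus rises by 13% to 32%. For a Group 2 result at 36 h to reach 0.2 IU/mL, the regular-schedule level at 24 h would have to be at least 0.2 / (multiplier x r(12)):

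- *t* = 5 h: 0.84 to 0.94 IU/mL
- *t* = 7 h: 0.50 to 0.56 IU/mL

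The Sample Size section gives 0.54 IU/mL as the highest level in the prior study, over samples taken from 23.25 to 32 h. A changed classification would therefore need a patient near that maximum together with the longest half-life considered.

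**The case against.** The strongest reply is that harm needs a long chain. The patient must be once-daily, a morning user, on the deferred route, in Group 2 and called after injecting. The instruction must then be understood as adding a dose, and the patient must do so. The protocol sets the time of a last dose under an existing prescription; it does not order an additional one. The instruction comes in a live conversation, where a patient who says that today's dose is taken would often be told not to repeat it. The forms not seen may also cover the case. A 19:00 dose would still be 36 h before a 07:00 surgery, anti-Xa is measured on arrival, and the anesthesiologist decides on any neuraxial block.

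Most of this stands, and it fixes the size of the point. A reader might infer that the plan directs some patients to take 3 mg/kg. The documents do not support that: they leave a contingency unaddressed. A reader might also infer that the dosing times are unworkable for once-daily users in general. That does not follow either, since a patient told in time can move the preceding dose.

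The reply does not remove the conflict itself. On the visible text, any sensible improvisation by the caller abandons the assigned time. The arrival check on day 0 does not protect the patient in the hours after a doubled dose on day -2. Because the preceding dose is not among the listed items, a doubled dose could also pass unnoticed.

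**Conclusion.** The point holds as a minor safety and adherence gap. On the deferred-consent route, the timing rules for the call and for Group 2 conflict for a once-daily user who has already injected that morning. The clock arithmetic is firm: 12 h for a 07:00 habit. The range of 9 to 13 h, and of 45 to 49 h if the patient stops, rests on the assumed habits of 06:00 to 10:00.

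The number affected is probably a handful at most: about 2 of 180 at the midpoints of the assumed ranges. The upper figure of about 10 needs every share at its maximum and should not be read as an estimate.

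A reader might infer bias in the time at which anti-Xa is reliably below 0.2 IU/mL. The working does not support that. An extra dose would change at most a rare classification. For patients who stop early or dose on day -1, the actual last-dose time is recorded, so the result can still be placed at its true interval. The effect on the primary threshold is negligible.

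**What to change.** In Subject Recruitment Methods, for once-daily users, do one of the following:

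- make the follow-up call no later than day -3; or
- do not randomise a once-daily user at the day -2 call if that day's dose has been taken.

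In either case, state that the assigned last dose replaces the usual dose and is never added to it, and put the same line in the call script.

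Recording the regimen and the time of the preceding dose on arrival is optional. No numeric minimum spacing between doses is proposed: it would rest on assumed habits and is a clinical judgement.

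The cost is a sentence or two of protocol text and one script line. The downside is one day less for once-daily patients to decide or, under the second option, a few late-consenting once-daily patients not randomised. Moving a dose also lengthens one interval: replacing a 07:00 dose by 19:00 on day -2 leaves 24 + 12 = 36 h since the day -3 dose. That already follows from Group 2's fixed time for any such patient who moves the dose, and the investigators should be content with it. The analysis does not change.

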### **Outcome Measure(s)**

The primary outcome of the study is the measurement of anti-Xa activity levels following the last treatment dose of enoxaparin in patients presenting for elective surgery. Anti-Xa level activity will be measured using a chromogenic assay and a hybrid curve calibrated to both heparin and enoxaparin. The randomization of patients to either the 24-hour group or the 36-hour group will allow for modeling, which will generate a prediction of the time point at which the level of anti-Xa activity can reliably be assumed to be lower than 0.2IU/mL.

Secondary outcomes will include determining the relationship of anti-Xa level activity over time (by using curve fitting or best-fit function) as well as attempting to determine if there are any patient conditions or characteristics that can predict delayed clearance of enoxaparin (elevated anti-Xa levels).

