### **Analytical Plan**

For the primary analysis, logistic regression of success criterion (anti-Xa activity level < 0.2 IU/mL) and 95% confidence limits at a success level (<0.2) of 95% likelihood will be utilized. For secondary analyses we plan to describe the best-fit function for anti-Xa activity levels over time. We also plan to explore clinical predictors for any anti-Xa activity levels > 1 standard deviation over the mean from the above function.

Protocol version:

Template updated 9.24.14

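### Elevation is judged against a curve in time alone, so patients given more enoxaparin per kg, or the once-daily regimen, are more likely to be labelled slow clearers at identical clearance

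*Combined protocol and SAP*

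**What the plan says.** The Outcome Measure(s) section lists, as a secondary outcome, an attempt to find patient features that predict "delayed clearance of enoxaparin (elevated anti-Xa levels"). The parenthesis makes a raised level the marker of slow clearance; clearance itself is not measured.

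The Analytical Plan gives the method in two steps. The first is to "describe the best-fit function for anti-Xa activity levels over time". The second is to "explore clinical predictors for any anti-Xa activity levels > 1 standard deviation over the mean from the above function". No dose, regimen or weight term is mentioned in the function, and the candidate predictors are not listed.

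Under Subjects selection criteria, patients may be on "treatment dose (1mg/kg twice daily or 1.5mg/kg daily) enoxaparin at the time of presentation for elective surgery". Under Interventions and Interactions, the team collects "demographic information recorded (age, weight, gender) as well as the enoxaparin dosage and the timing of their last administration". One blood draw is taken, after which participation ends.

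**The concern.** With one sample per patient, a level above a time-only curve can mean that drug was removed slowly or that more drug was given. The two cannot be told apart unless dose is in the reference curve. The eligible regimens differ by 1.5 to 1 in mg/kg of the last injection, and actual mg/kg may vary further within a regimen if doses are rounded.

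The flagged group is then enriched for higher dose per kg and for once-daily use. Regimen, weight or dose rounding may be reported as predictors of delayed clearance when clearance does not differ. A patient with slow clearance but a lower dose per kg is less likely to be flagged. The stake is the secondary message about which patients clear enoxaparin slowly.

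**Working it through.** The plan gives no figure for this secondary analysis, so there is none to reproduce. Its precision figure (150 patients, threshold about 29 h, limits about 28 h and 33 h) belongs to the primary logistic analysis and plays no part here.

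**Inputs from the documents.** Two regimens, 1 mg/kg twice daily and 1.5 mg/kg daily; last dose nominally 24 h or 36 h before surgery; one sample; a flag at more than 1 SD above the level-time function.

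**Inputs assumed, because the documents do not give them.** First-order elimination with half-life h of 5 to 7 h; 20% of patients on the once-daily regimen; log-SD of the elimination rate 0.1 to 0.3; log-SD of dose per kg 0.1; residual log-SD 0.2; draws spread over 8 h after 24 h or 36 h. The distribution of clearance is the same in both regimens.

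**Step 1: level ratio at equal time since the last dose.** With k = ln 2 / h, the once-daily to twice-daily ratio at steady state is

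R = 1.5 × (1 − e^(−12k)) / (1 − e^(−24k)) = 1.5 / (1 + 2^(−12/h)).

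- h = 5 h: 1.5 / (1 + 0.190) = 1.26
- h = 7 h: 1.5 / (1 + 0.305) = 1.15

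Without accumulation the ratio is 1.5. Accumulation narrows the gap because the twice-daily regimen has the smaller injection but the larger daily total (2 against 1.5 mg/kg). R stays above 1 for any half-life under 12 h. Within one regimen the level is proportional to dose per kg, so a 1.5-fold difference there equals log2(1.5) = 0.585 half-lives: 2.9 h of elimination at h = 5 h and 4.1 h at h = 7 h.

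**Step 2: the shift against the spread.** Variation in elimination rate is multiplied by time, so its contribution to the log-scale spread is about k × t × log-SD. At h = 5 h and t = 24 h, k × t = 3.33.

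- log-SD 0.1: total spread √(0.33² + 0.1² + 0.2²) = 0.40. The shift ln 1.26 = 0.23 is 0.58 SD.
- log-SD 0.3: total spread √(1.00² + 0.1² + 0.2²) = 1.02. The same shift is 0.23 SD.

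The size of the problem therefore depends mainly on between-patient variability.

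**Step 3: flag rates by simulation.** Steady state, log-scale curve quadratic in time, flag above +1 SD of the residuals:

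| Half-life | log-SD of elimination rate | Time only: once daily v twice daily | Ratio | Dose and regimen in curve: once daily v twice daily |
|---|---|---|---|---|
| 5 h | 0.1 | 23.9% v 13.1% | 1.8 | 14.3% v 15.4% |
| 5 h | 0.2 | 18.7% v 13.7% | 1.4 | 13.5% v 14.9% |
| 5 h | 0.3 | 16.2% v 13.2% | 1.2 | 12.5% v 14.1% |
| 7 h | 0.1 | 21.2% v 14.0% | 1.5 | 14.2% v 15.7% |
| 7 h | 0.2 | 17.1% v 14.2% | 1.2 | 13.3% v 15.1% |
| 7 h | 0.3 | 15.2% v 13.9% | 1.1 | 12.5% v 14.6% |

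Adding dose and regimen removes the excess flagging of once-daily users. A difference of one to two points the other way remains, because slow elimination spreads levels more under the shorter dosing interval.

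**Step 4: sensitivity.** The plan does not fix the scale of the curve. On the original scale, at steady state, the time-only ratios are 1.1 to 1.9. If accumulation is ignored, the log-scale ratios are 1.7 to 4.1 (20% to 39% against 10% to 12%), but that sets aside repeated dosing.

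**The case against.** The plan partly defines its own term: what it operates on is an elevated level, and the study's objective concerns residual activity below 0.2 IU/mL. For that purpose a patient with a high residual level matters whatever the cause. This stands, and it makes the label as much at fault as the model. It does not rescue a claim about clearance.

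Dose and weight are recorded and the clinical predictors are not listed, so dose could be examined at the second step, jointly with other candidates. That also stands: dose is neither named nor excluded. But under the present wording, a dose effect found there would be reported as a predictor of delayed clearance, and weight would stay confounded with dose unless both were in the model.

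The analysis is secondary and exploratory. That is correct, and it limits the weight of the point.

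Three stronger readings might be inferred, and none is supported:

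- *That higher-dose patients are simply counted as slow clearers.* At steady state, 76% to 85% of once-daily users are not flagged. On the log scale, under 2% of all flagged patients had faster-than-median elimination.
- *That the excess is as much as 3.7-fold at steady state.* That figure needs a total log-SD as low as 0.35 with a short half-life. At h = 4 h and 24 h, k × t = 4.16, so 0.35 / 4.16 leaves a variation of only about 8% in elimination rate and nothing for assay or absorption. A 20% variation alone gives 0.20 × 4.16 = 0.83. At a log-SD of 1.0 the ratio falls to 1.2 to 1.55.
- *That regimen will emerge as a false predictor.* With 150 patients and a Fisher test, at a total log-SD of 1.0, it reaches p < 0.05 in about 5% to 15% of trials. The chance passes 50% only at log-SD 0.35 with a 4 to 5 h half-life.

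**Conclusion.** The concern holds as a matter of the stated method. A rule that judges elevation against time alone, and then calls the excess delayed clearance, mixes dose with clearance when regimens differ 1.5-fold per injection and each patient is sampled once. At identical clearance, once-daily users are more likely to be flagged, by about 1.1 to 1.8 times (15% to 24% against 13% to 14%). This range rests on steady state, a half-life of 5 to 7 h, 20% once-daily use and the assumed variabilities; none of these is in the documents. At steady state, materially higher ratios need small between-patient variability and a short half-life. False predictors are possible, not certain.

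A reader might also infer that the primary result is biased by this. It is not: the logistic threshold and the sample size of 150 do not use the level-time curve or the flag. The change is worth making because it is nearly free, but it concerns a secondary, exploratory aim.

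**What to change.** Amend the secondary part of the Analytical Plan before the data are examined:

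1. Include actual dose per kg (recorded dose divided by recorded weight) and regimen in the level-time model. Regimen is needed as well as mg/kg because accumulation differs between dosing intervals.
2. Define the excess level from that model's residuals, and look for other predictors of that excess.
3. Report dose per kg and regimen as predictors of residual level in their own right. This keeps the answer to the practical question of who still has a high level.
4. In the Outcome Measure(s) section, describe the result as a higher residual level for a given dose, regimen and time. Even after adjustment, one sample per patient cannot show clearance directly.

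The cost is a few sentences and two model terms, with no extra patients, visits or samples. Dose and weight are already collected; check that the data collection form also captures dosing frequency, which eligibility already requires the team to know. The downside is an imprecise regimen term if few once-daily users enrol.
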